### 7.2 Primary and Secondary Endpoints/Outcome Measures

The primary outcomes to be assessed will be length-of-stay, in-hospital, short-term (30-day), and long-term (1- year) mortality.

Secondary outcomes include: long-term complications, such as re-admission to hospital, additional abdominal surgery and the development of new medical conditions as well as the relationships between any of these outcomes and patient characteristics.

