### **8. SAMPLE SIZE**

This study will identify patients diagnosed with an intestinal emergency who may require surgery and observe patient outcomes, and how they correlate with the treatment they received. Trial analysis of all admissions in 2018 identified 901 patients with an abdominal emergency, 59% (530) of which had surgical intervention, either a laparotomy or a laparoscopy. Scaling these numbers to the study period of 6.5 years, we expect to identify a total of over 5,800 patients with an intestinal emergency and over 3,400 patients undergoing surgery. All UK hospitals have to submit data on all their intra-abdominal procedures to the National Emergency Laparotomy Audit (NELA). From previous analysis of PHUT NELA data (11), at least 30% of patients having an operation will have been completed laparoscopically. This is a remarkably large proportion of laparoscopic procedures compared to the UK average (8% according to NELA database) and will provide us over 1,000 laparoscopies in our study data set.

The PHUT data set includes a sufficient number of outcomes for model development (rule of thumb: 10 outcomes per predictor variable (25)). This study will be looking at a patient population with high mortality. Initial analysis of 2018 data identified in-hospital mortality as the rarest outcome with 23 deaths (4.3%) of patients having surgery and 28 deaths (7.6%) of patients not having surgery. Other outcomes occur in greater numbers. Collective numbers for the 6.5 year study period will therefore provide us with enough outcomes for the development of logistic regression models. The data set will be tested for separation and Firth's correction applied if necessary (26). Based on these numbers, we will be able to establish statistically significant correlations from this data set from a single hospital.

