### 10.2 Data analysis

Extracted data will be cleaned and quality controlled prior to analysis to ensure all relevant patients have been extracted. Given that our analysis will use only routinely collected, clinical data, missing values are unlikely to pose an issue. Initial analysis of 2018 data confirmed that clinical data within 24h of admission was almost fully complete for a remarkable >97% of admissions, meaning there is likely no need to impute data. We will test whether excluding admissions with missing data will introduce bias.

Our analysis can be broken down into the following steps:

- Comparison of the four treatment groups based on demographics, outcomes and medical pathway. This will include calculating mortality and long-term complication rates (Objective 2).
- Construct and compare risk models for each treatment group to predict short-term and long-term risk and to investigate the effect of both patient and hospital-level factors on outcome (Objective 3).

- Identify patients in each group who are abnormal for the group and might have fared better with a different treatment, using clustering algorithms (Objective 4).

After splitting the data set into subsets for each of the four patient groups using diagnosis and procedure codes (see above), mortality and long-term complication rates will be calculated for each group. Longer-term follow-up will include rates of re-admission to hospital, additional theatre visits and development of new medical conditions, within one year of initial admission with an abdominal emergency. Results will provide updated estimates of the average risks of different surgical procedures as well as the risk of not having surgery. Results will be compared with P-POSSUM mortality. Patient groups will further be characterised the using patient factors. Parameters of interest will include but are not limited to age, sex, mortality, long-term complication rates, admission early warning scores (NEWS, LDTEWS and LDTEWS:NEWS), frailty, medical history (previous ICD-10 codes).

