Patient group characteristics will be summarised with proportions for nominal and ordinal variables, means and standard deviations for continuous variables having symmetric unimodal distributions, and medians and interquartile ranges for other continuous variables. Clinical outcomes will be reported as proportions with 95% confidence intervals. Statistical tests of differences in proportions (Chi - nominal variables) and means/medians (ANOVA/Kruskal-Wallis) will be performed. Post-hoc pairwise comparisons will be carried out using Scheffe's method for ANOVA and Dunn's test for Kruskal-Wallis results and Bonferroni corrections for Chi results with significance at  $p < 0.05$ .

In the next step, we will identify which patient characteristics affect the outcome for a specific care pathway. Candidate predictor variables of 30-day mortality will be assessed with simple univariable linear regression and check for non-linearity. For each treatment group, we will construct a logistic regression model with the candidate predictor variables and non-linear terms as needed. Logistic regression performance will be tested using "goodness of fit" and discrimination. Goodness of fit, the ability to correctly predict risk, will be evaluated using the Hosmer-Lemeshow statistic (28) and by 10-fold cross-validation. Discrimination, the ability to rank cases in terms of risk, will be assessed using the Area Under the Receiver Operating Characteristic Curve (AUROC) (29). The relative importance of individual parameters will be assessed by the parameters Wald and t-statistics.

The last objective is to determine outlier clusters of patients who might have fared better on a different care pathway. For each treatment group, machine learning classification algorithms will be used to identify homogenous clusters of admissions in terms of their attributes. Each clustering will be reported by its method, number of clusters and intracluster correlation coefficients (ICCs) with 95% confidence intervals and used to extend the logistic regression risk model for the treatment group to see if the model is improved as measured by a likelihood ratio test. Where this is the case the patient subgroups corresponding to the clusters will be analysed in terms of their clinical characteristics.

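### Length of stay, listed as a primary outcome, falls under a group comparison that counts death in hospital the same as live discharge, so the result cannot be read as a difference in recovery time

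*Protocol*

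**What the plan says.** Protocol section 7.2 states: "The primary outcomes to be assessed will be length-of-stay, in-hospital, short-term (30-day), and long-term (1- year) mortality". The Outcomes paragraph of section 10.1 repeats this. The synopsis is narrower and gives mortality risk per treatment group as the primary endpoint, so the primary status of length of stay rests on 7.2 and 10.1.

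The first analysis step in section 10.2 is "Comparison of the four treatment groups based on demographics, outcomes and medical pathway". Section 6.2 names the four pathways as laparotomy, laparoscopy, other alternative treatment and end of life care.

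For between-group testing, section 10.2 assigns Chi-squared to nominal variables. For continuous variables it says tests of "means/medians (ANOVA/Kruskal-Wallis) will be performed", followed by "Scheffe's method for ANOVA and Dunn's test for Kruskal-Wallis results" for pairwise comparisons at p < 0.05. It also says "Clinical outcomes will be reported as proportions with 95% confidence intervals", a format that does not fit a duration.

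No section says how a stay that ends in death enters the length-of-stay comparison.

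**The concern.** A hospital stay ends in one of two ways, live discharge or death. A rank test or ANOVA on the recorded duration treats both as the same event, so a patient who dies on day 3 and one who recovers and goes home on day 3 contribute the same value.

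This would matter little if mortality were similar across groups. The protocol expects the opposite. Section 8 gives 2018 in-hospital mortality as "23 deaths (4.3%) of patients having surgery and 28 deaths (7.6%) of patients not having surgery". Section 4.1 cites 30-day mortality of 63% without laparotomy against 13% with it. One of the four groups is defined by care at the end of life.

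A significant result on this outcome could therefore reflect a difference in recovery time, in the risk of death, in the timing of death, or any mixture of these. The planned test cannot separate them.

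**Working it through.** **1. The protocol's own figures.** Section 8 reports 901 patients in 2018, 530 of them with surgery, so 901 − 530 = 371 without.
- In-hospital mortality: 23/530 = 4.34% (stated 4.3%) and 28/371 = 7.55% (stated 7.6%).
- Over 6.5 years: 901 × 6.5 = 5,856.5 (stated as over 5,800) and 530 × 6.5 = 3,445 with surgery (stated as over 3,400). This leaves 371 × 6.5 ≈ 2,411 without surgery.

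These figures reproduce, apart from rounding in the 7.6%.

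**2. What must be assumed.** The protocol gives neither a length-of-stay distribution nor the timing of deaths. As an illustration, let time to live discharge be lognormal with median 12 days and log-SD 0.7, identical in every group. Let time to death be lognormal with log-SD 0.8 and median d. If a proportion p of a group dies in hospital, the observed median stay m solves

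p · Φ[ln(m/d)/0.8] + (1 − p) · Φ[ln(m/12)/0.7] = 0.5.

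Check for p = 0.63 and d = 4, at m = 6.05: 0.63 × 0.697 + 0.37 × 0.164 = 0.439 + 0.061 = 0.50.

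**3. Observed median stay (days), with identical discharge times in every group.**

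| In-hospital mortality p | d = 4 | d = 12 | d = 20 |
|---|---|---|---|
| 4.3% | 11.6 | 12.0 | 12.2 |
| 7.6% | 11.3 | 12.0 | 12.4 |
| 13% | 10.8 | 12.0 | 12.7 |
| 63% | 6.0 | 12.0 | 16.3 |

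- With early deaths, the 2018 rates give 11.6 − 11.3 = 0.3 days, and 13% against 63% gives 10.8 − 6.0 = 4.8 days.
- When deaths and discharges share the same median, the difference in medians disappears.
- With late deaths it reverses: 16.3 − 12.7 = 3.6 days longer in the high-mortality group.

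The 13% and 63% are borrowed as assumed in-hospital values. In the protocol they are 30-day figures from a cited study, and only in-hospital death cuts a stay short.

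**4. Effect on the test.** A separate two-group simulation used other assumptions: discharge lognormal with median 8 days, identical in both groups; median time to death 2, 3 or 5 days; both log-SDs 0.8; 400 runs per scenario; Kruskal-Wallis at 0.05. In patients who died, the stay was the smaller of the two times.

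| Scenario | Runs with p < 0.05 | Median stay, days (death at median 3 days) |
|---|---|---|
| 3,445 at 4.3% vs 2,411 at 7.6% | 18% to 41% | 7.7 vs 7.5 |
| 3,445 at 4.3% vs 2,411 at 20% | 100% | 7.7 vs 6.5 |
| 3,445 at 4.3% vs 200 at 30% | 90% to 99% | 7.7 vs 5.8 |
| 3,445 at 4.3% vs 200 at 63% | 100% | 7.7 vs 3.8 |

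The ranges run over the three death timings. The group of 200 and the mortalities of 20% and above are assumptions. Measured against equality of discharge times, the nominal rate is 5%. Restricting the test to patients discharged alive brought it back to about 3% to 7%, but only because death was simulated independently of the time the patient would otherwise have taken to leave.

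**The case against.** **The link to the test is inferred.** The test sentence in 10.2 does not name length of stay, and the paragraph opens with group characteristics. This is so. But length of stay is the only continuous primary outcome and these are the only between-group tests given for continuous variables. A statistical analysis plan could add a rule for deaths. The protocol has nevertheless already chosen the test and the post-hoc procedures, so this is a method poorly fixed and not merely detail left for later.

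**Duration with deaths included is a legitimate quantity.** Total bed use is a fair description, and 10.2 reports mortality for the same groups, so a reader would see a short stay next to many deaths. This stands for description. The rejection rates above are false positives only if the question is recovery time. It does not rescue the test, whose p-value still has no single interpretation.

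**The size rests on assumptions.** This stands in full. At the protocol's own in-hospital rates the shift in medians is small, and its direction depends on when deaths occur.

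**Two stronger readings are tempting but unsupported.** A reader might infer that care pathways will be chosen from length of stay. Section 6.2 (Objective 3) and the synopsis base that choice on models for the risk of death, and the outcome named for model building in 10.2 is 30-day mortality. A reader might also infer that comparing "rates of re-admission to hospital, additional theatre visits and development of new medical conditions, within one year of initial admission" by Chi-squared is invalid because dead patients cannot be re-admitted. The crude proportion is a valid cumulative incidence, and 10.2 already calculates it alongside mortality for each group.

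**Conclusion.** The concern holds for length of stay. As written, the comparison combines mortality and recovery time in groups that are expected to differ in mortality, so it cannot be interpreted as a difference in recovery. A high-mortality group need not look shorter; that follows only if deaths come early.

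The size is conditional. With early deaths it is about 0.3 days in the median at the 2018 rates, and several days in a group where most patients die in hospital. End of life care is the group where that is most plausible, but the protocol gives no in-hospital mortality for it. Even the small shift can reach significance at the projected numbers.

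The analyses that inform the care pathways are not affected, because they model death. The change is worth making because the outcome is listed as primary and the remedy is cheap.

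**What to change.** In section 10.2, name the analysis of length of stay explicitly: time from admission to live discharge, with in-hospital death as a competing event, presented as the cumulative incidence of live discharge by treatment group.

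Add stay reported separately for patients discharged alive and patients who died in hospital. Label this descriptive only, because it conditions on survival, which itself differs between groups.

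State that the proportion format for clinical outcomes does not apply to length of stay.

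Optionally, add a composite of death or re-admission to the one-year complication rates. This helps reading and corrects no error.

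Cost: a few lines of text and minor programming. Section 9.1 already plans to link length of stay and in-hospital mortality, so no new data are needed. The downside is a summary slightly less familiar to clinical readers than a single median.

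### Protocol Section 10.2 puts three post-hoc procedures under one 0.05 threshold, names no adjustment for Dunn's test, and does not say whether 0.05 is per comparison or family-wise

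*Protocol*

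**What the plan says.** The first analysis step in Section 10.2 is: "Comparison of the four treatment groups based on demographics, outcomes and medical pathway". Omnibus tests come first: Chi-squared for nominal variables, and for the rest "means/medians (ANOVA/Kruskal-Wallis) will be performed".

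One sentence then fixes the pairwise follow-up. It gives Scheffé's "method for ANOVA and Dunn"'s "test for Kruskal-Wallis results and Bonferroni corrections for Chi"-squared, with a single significance level of 0.05. It does not say whether Dunn p-values are adjusted, whether 0.05 applies to each pair or to the set of pairs, or whether the test is two-sided. The term post-hoc suggests that pairs are tested only after a significant omnibus result, but no rule says so.

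Section 7.2 states: "The primary outcomes to be assessed will be length-of-stay, in-hospital, short-term (30-day), and long-term (1- year) mortality". Section 10.2 does not say which test length of stay receives. Group characteristics that are not symmetric and unimodal are summarised by "medians and interquartile ranges for other continuous variables". Clinical outcomes are to be given as proportions, which does not suit length of stay.

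**The concern.** The sentence names an explicit correction for one of its three procedures. An analyst who takes it literally will divide 0.05 by six for the Chi-squared pairs and leave the Dunn pairs as they come. Another will assume that Dunn's procedure carries its own Bonferroni-type adjustment. Both can claim to follow the protocol, and they can disagree on any pair with an unadjusted p-value between about 0.01 and 0.05.

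On the literal reading, the same nominal threshold gives different protection depending on a variable's type and distribution. The variables most likely to go to Dunn's test are skewed ones, and length of stay is usually skewed. Section 6.1 intends the results to inform care pathways and conversations with patients, so a claim that one pathway gives a shorter stay than another is one that readers may use.

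The lesser matter is efficiency. Scheffé protects every possible contrast among four means although the sentence plans only pairs, and Bonferroni can be replaced by a procedure that never rejects fewer pairs.

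**Working it through.** **Inputs**
- Groups: 4 (Section 10.2), so 4 × 3 / 2 = 6 pairs per variable.
- Level: 0.05 (Section 10.2); two-sided is assumed.
- Group sizes: not given. Section 8 gives 901 patients in 2018, 530 of them operated on, at least 30% of operations laparoscopic, and 6.5 years. Reproducing its scaling: 901 × 6.5 = 5,856.5; 530 × 6.5 = 3,445; 0.30 × 3,445 = 1,033.5. These agree with "we expect to identify a total of over 5,800 patients with an intestinal emergency and over 3,400 patients undergoing surgery" and with over 1,000 laparoscopies. The four sizes were assumed either equal (1,465 each) or unequal (2,410/1,034/2,000/410); the split of the non-operated patients is an assumption.
- The protocol states no family-wise error rate, so there is no figure of its own to reproduce here.

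**Dunn's test, if unadjusted (critical z 1.960)**

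For *m* equal groups of equal size, the large-sample chance of at least one false pair is P(Q_m > 1.960 × √2), where Q_m is the studentized range with infinite degrees of freedom. For two separate equal pairs it is 1 − 0.95² = 9.75%.

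| True state | No Kruskal-Wallis gate | Gate at 0.05 |
|---|---|---|
| All four equal | 20.3% | 5.0% |
| Three equal, one clearly different | 12.2% | 12.2% |
| Two equal pairs | 9.8% | 9.8% |
| One equal pair only | at most 5% | at most 5% |
| All four different | no null pair | no null pair |

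The independence bound for six tests is 1 − 0.95⁶ = 26.5%. The gate gives no protection in the second and third rows because the real difference opens it. Large-sample simulation (400,000 replicates) with the unequal sizes gave 12.1% and 9.7% for those rows. Rank-based Dunn simulations on rounded log-normal data with ties (about 1,000 patients, 4,000 replicates each), counting only runs where Kruskal-Wallis was significant, gave 10.5 to 12.1% and 8.5 to 9.4%.

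**Dunn's test, if adjusted by Bonferroni**

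Per-pair level 0.05/6 = 0.0083, critical z 2.638. With equal groups the family-wise error is 4.1% with all four equal (3.8% gated) and 2.3% with three equal and one different, so it stays below 5%. With Holm, the three-equal case came out at 3.6 to 4.5%.

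**Scheffé against Tukey-Kramer for six pairs**
- Scheffé critical value: √χ²(0.95; 3) = 2.795. Family-wise error P(Q₄ > 2.795 × √2) = 2.7% with all four equal (2.5% with the unequal sizes), and 1.4% with three equal and one different.
- Tukey-Kramer critical value: 2.569, family-wise error about 5%.
- A pair with 80% power under Tukey-Kramer has a standardised difference of 2.569 + 0.842 = 3.411. Under Scheffé its power is Φ(3.411 − 2.795) = Φ(0.616) ≈ 73%.

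**Bonferroni against Holm**

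Holm rejects every pair that Bonferroni rejects, at the same family-wise level. Example: means 0/0.12/0.3/0.5 SD and assumed sizes 2,400/1,030/1,800/600. The closest pair has z = 0.12 / √(1/2,400 + 1/1,030) = 3.22. Bonferroni power is Φ(3.22 − 2.638) ≈ 72%. Under Holm the other five pairs are almost always rejected first, so this pair is tested near 1.960 and its power is about 89%.

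**The case against.** The sentence can be read as a list giving each omnibus test its own multiple-comparison method, with Bonferroni named for Chi-squared only because Chi-squared has no named post-hoc test. Dunn's procedure is often run with a built-in adjustment, and the choice of adjustment is commonly left to the SAP, which is not at hand. This stands in part. The protocol nowhere says that Dunn p-values are unadjusted, so a reader who infers that Dunn's pairs definitely run at 12% goes further than the text. What remains is that the protocol settled the adjustment for one procedure and was silent on another in the same sentence.

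The 12% also needs exactly three equal groups and one different. Laparotomy, laparoscopy, other treatment and end-of-life care may all differ, in which case no pair can be falsely declared different. That is right: 12% is the worst gated case among those examined, not an expected rate.

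A reader might set 12% for Dunn beside about 2.5% for Scheffé. Those figures belong to different true states. On a common footing they are 12.2% against 1.4% (three equal, one different), or 5.0% gated and 20.3% ungated against 2.7% (all equal). Nor can the 12% be called more than twice the stated error rate, because the protocol states no family-wise rate.

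Scheffé and Bonferroni both control family-wise error. Calling either a mistake would be wrong, and with more than 5,800 patients expected the power lost will seldom matter. The synopsis gives mortality risk as the primary endpoint. Mortality is a proportion, and its pairwise tests are Bonferroni-corrected as written. The route from length of stay to Dunn's test is inferred. Finally, these are the descriptive comparisons of Objective 2 in a retrospective cohort; the logistic models of Objective 3 do not depend on them. All of this keeps the severity low.

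**Conclusion.** The point holds as a minor ambiguity with a modest efficiency loss attached. The protocol leaves open whether Dunn's six p-values are adjusted and what 0.05 refers to. The error rates above 5% in the working apply only if Dunn p-values are left unadjusted; with Bonferroni or Holm over the six pairs there is no inflation. The effect on length of stay is probable rather than documented. The Scheffé and Bonferroni choices are valid, and replacing them buys some power at the same 5% family-wise control.

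These figures assume two-sided tests, large samples and group sizes that the protocol does not give. The three-equal result hardly moves between the two sets of sizes (12.2% and 12.1%).

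**What to change.** Replace the post-hoc sentence in Section 10.2 with:

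> Post-hoc pairwise comparisons will use Tukey-Kramer after ANOVA, and Holm-adjusted p-values over the six pairs for Dunn's test after Kruskal-Wallis and for pairwise Chi-squared tests; adjusted p < 0.05 (two-sided) is significant, family-wise per variable.

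The part that matters most is the stated adjustment for Dunn's test and the family-wise definition of 0.05. Moving to Tukey-Kramer and Holm is a free gain for pairs. If a pooled contrast is wanted, such as laparotomy against all other patients (the first output in Section 15.1), it should be specified separately, since Tukey-Kramer as written here covers only pairs.

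The cost is one sentence and a software option. If Dunn p-values would otherwise have been unadjusted, some pairs with unadjusted p between about 0.01 and 0.05 may no longer be called significant. If they would have been Bonferroni-adjusted, nothing is lost.

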### **6.2 Objectives**

1. Identify all patients with a condition that would qualify them for emergency abdominal surgery, both laparotomy and keyhole (laparoscopic) procedures, regardless of whether they had surgery

or not. This will be done by filtering electronic hospital records for appropriate diagnosis and operation codes.

2. Provide updated estimates of the average risk of death for different treatment options, including surgical and non-surgical intervention, using statistical analysis of short-term and long-term outcomes. Describe health characteristics of the typical patient population receiving one of the treatment options, based on their clinical data and an established risk index.
3. Logistic regression will be used to predict the risk of death for each patient group and each treatment option, which will allow identification of the best care pathways given a patient's health characteristics.
4. Identify patients who would have likely benefited from a different care pathway than the one they received, using machine learning classification algorithms

Our analysis will form the foundation for the establishment of four well-defined care pathway options, each with the patient's best interest in mind: laparotomy, laparoscopy, other alternative treatment, and end of life care.

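### Section 10.2 screens predictors of a yes/no outcome with linear regression, so non-linearity is checked on a different scale from the logistic models that use the result

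*Protocol*

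**What the plan says.** Protocol Section 10.2 sets out the modelling in two consecutive sentences. The first covers screening: "Candidate predictor variables of 30-day mortality will be assessed with simple univariable linear regression and check for non-linearity". The second covers the model itself: "For each treatment group, we will construct a logistic regression model with the candidate predictor variables and non-linear terms as needed".

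The finished model is then judged as follows: "Goodness of fit, the ability to correctly predict risk, will be evaluated using the Hosmer-Lemeshow statistic (28) and by 10-fold cross-validation". Discrimination is measured by AUROC.

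Elsewhere the model for death is consistently logistic. Objective 3 in Section 6.2 reads "Logistic regression will be used to predict the risk of death for each patient group and each treatment option". Sections 7.1, 7.3 and 8 also name logistic regression. No section justifies a linear model for a binary outcome or places the non-linearity check on the log-odds scale. Length of stay is a continuous outcome in this study, but the screening sentence names 30-day mortality.

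**The concern.** Whether a predictor's effect is straight depends on the scale. When risk is low, an effect that is straight in log-odds bends upward in probability. A check made in a linear regression therefore tests a different assumption from the one the logistic model makes. Two errors follow:

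- It tends to flag upward curvature that the logistic model does not need.
- It can miss downward curvature in log-odds, because the two bends cancel on the probability scale.

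Unneeded terms cost most where deaths are few. Models are fitted separately by treatment group, and Section 8 relies on 10 outcomes per predictor. Age and the early warning scores are the sort of graded predictors for which the mismatch could matter. Objective 3 uses these models to choose between care pathways.

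**Working it through.** **1. Group sizes and deaths (Section 8).**

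- Surgical patients: 530 × 6.5 = 3,445, which agrees with the protocol's figure of over 3,400.
- Laparoscopy: the protocol expects "at least 30% of patients having an operation will have been completed laparoscopically", so 0.30 × 3,445 ≈ 1,033, which agrees with over 1,000.
- Laparotomy: 3,445 − 1,033 = 2,412.
- Mortality: the 2018 pilot gives "in-hospital mortality as the rarest outcome with 23 deaths (4.3%) of patients having surgery and 28 deaths (7.6%) of patients not having surgery", so 23/530 = 4.34% for surgery.
- Deaths at that rate: 1,033 × 0.0434 ≈ 45 and 2,412 × 0.0434 ≈ 105. At 10 outcomes per predictor, 45 deaths support about 4 parameters.

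**2. Assumptions.** The protocol gives no test, effect size or curvature. Take one standard normal predictor x with logit(p) = a + bx + cx², where a is set to give 4.34% mortality in each group. Pilot in-hospital mortality stands in for 30-day mortality. The x² term is tested at 5%, by a least-squares t-test (linear check) or by a logistic likelihood ratio test (logistic check). Each setting uses 2,000 simulated data sets.

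**3. Why the checks differ.** For a rare outcome, p is close to exp(a + bx + cx²). The quadratic term that linear regression estimates then has the sign of s² + (b·s²)² − 1, where s² = 1/(1 − 2c). At an odds ratio (OR) of 2 per SD, b = 0.693:

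- c = 0: 1 + 0.480 − 1 = +0.48. There is no curvature in log-odds, yet the linear check sees an upward bend.
- c = −0.1: 0.833 + 0.334 − 1 = +0.17. The true curvature is downward, but the check sees upward.
- c = −0.2: 0.714 + 0.245 − 1 = −0.04. The bends nearly cancel, which is the check's blind spot.

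**4. How often x² is flagged, linear / logistic.**

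| True curvature c | OR per SD | n = 1,033 | n = 2,412 |
|---|---|---|---|
| 0 (false flags) | 1.2 | 5% / 6% | 6% / 5% |
| 0 | 1.5 | 13% / 5% | 20% / 6% |
| 0 | 2 | 47% / 6% | 77% / 5% |
| −0.2 | 1.2 | 18% / 37% | 50% / 67% |
| −0.2 | 1.5 | 9% / 37% | 30% / 69% |
| −0.2 | 2 | 3% / 34% | 5% / 67% |
| −0.4 | 1.2 | 59% / 80% | 97% / 99% |
| −0.4 | 2 | 23% / 77% | 65% / 99% |
| +0.2 | 1.2 | 73% / 56% | 97% / 91% |
| +0.2 | 2 | 99% / 40% | 100% / 74% |

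Upward curvature is not missed. At c = −0.1 and OR 2, the linear check reports an upward bend, the wrong direction, in 12% (n = 1,033) and 20% (n = 2,412).

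**5. Other mortality rates in the protocol.** For laparotomy at 9.5% and 13%, false flags from the linear check are 27–28% at OR 1.5 and 92–93% at OR 2. Curvature of −0.2 is found as follows, linear against logistic: 88–95% against 95–97% at OR 1.2, 64–81% against 93–98% at OR 1.5, and 10–14% against 91–97% at OR 2.

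**6. Is there a backstop?** With c = −0.2 left out of the logistic model, the Hosmer-Lemeshow test (10 groups, 8 df) rejects in 9–11% for laparoscopy and 19–26% for laparotomy. Cross-validation was not simulated.

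**7. Effect on predicted risk.** If c = −0.2 at OR 2 is missed, the best straight-line logistic fit gives 6.3% against a true 7.0% at +1 SD, and 10.0% against 7.6% at +2 SD. About 2% of patients lie beyond +2 SD.

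The two non-surgical groups were not simulated, because the protocol gives no split between them.

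**The case against.** **It is probably a one-word slip.** Every risk model elsewhere in the protocol is logistic. This is plausible, and if so the analysts may do the right thing anyway. The sentence still states a method, and it would be carried forward by anyone who follows it.

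**The protocol does not describe the check.** It gives no test or threshold and does not say that the check is made inside the linear regression. The next sentence asks for "we will construct a logistic regression model with the candidate predictor variables and non-linear terms as needed", and need could be judged there in log-odds. Screening details may also belong in an analysis plan, which was not available. This stands as a limit on the figures, which describe an assumed check. It does not remove the mismatch, because the named method is wrong rather than missing.

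**The figures depend on the assumed standard error.** Robust (HC3) standard errors cut false flags at OR 1.5 to 6% (n = 1,033) and 11% (n = 2,412), and raise detection of −0.2 at OR 1.2 and 1.5. That stands. At OR 2, false flags remain at about 24–27% and 63–67% over two runs, and detection of −0.2 stays near 10%.

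**The practical effect is small.** A falsely added term is re-estimated near zero in the logistic model, and mean risk error then changes by only 0.01–0.04 percentage points. That also stands for false flags. With −0.2 curvature, the linear rule does about as well as a straight-line model or better, but the fair comparator is a logistic check. Against that, at n = 2,412, mean risk error is 0.72 against 0.60 points (OR 1.5) and 0.77 against 0.62 points (OR 2).

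**The scarcity argument uses in-hospital deaths.** Section 8 calls these the rarest outcome, so 30-day deaths may exceed 45 in the laparoscopy group. This is fair, and the figure should be read with that caveat.

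**Conclusion.** The point holds and should be fixed. As written, the protocol screens a binary outcome with linear regression and passes the resulting non-linear terms to logistic models. That mismatch needs no simulation to establish.

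Its size rests on the assumed test, effect sizes, curvature and 4.3% mortality. It is negligible for false flags at OR 1.2 per SD, moderate at 1.5 and large at 2. Detection of moderate downward curvature falls at all three.

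The consequences are bounded. Screening for association is nearly unaffected, binary predictors are untouched, upward curvature is not missed, and the mortality rates and group comparisons do not change. What is at risk is the shape of continuous predictors in the group-specific risk models. Hosmer-Lemeshow is a weak safeguard for that, and the protection from cross-validation is unknown.

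**What to change.** In Section 10.2, replace the linear regression in the screening sentence with univariable logistic regression. Add that non-linearity of continuous predictors is checked on the log-odds scale within each treatment group, for example by a likelihood ratio test of a spline or fractional-polynomial term against the linear term. If linear regression was meant for length of stay, say so in a separate sentence. The cost is one sentence of protocol text, with no extra data or analysis effort.
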